Related to the capacity aim, the Community Advisory Board (CAB) includes about 20 local Dan River Region health care and community partners and academic researchers. Some members of the CAB will be responsible for screening, recruit, enrollment/data collection, and program implementation and are included as study investigators. The Parent Advisory Team (PAT) includes about 15 parents who are past iChoose program participants who will serve in a similar role as a community health worker or patient navigator. They will be asked to assist in distributing recruitment materials for our open referral/enrollment process, help potential families understand both programs and timing of the intervention sessions, and ask to promote program adherence and provide a program 'safety net'. This will include contacting enrolled families and supporting their needs to successfully engage in the program. Both the PAT and CAB groups will meet monthly (e.g. using a mix of in-person and conference call meetings) and use a shared-decision making and participatory agenda meeting structure to guide all aspects of the study. As a part of this process, those who volunteer and sign informed consent will also participate in annual mixed-methods evaluation to assess capacity and engagement. Patient and stakeholder engagement and evaluation is a requirement of our funder.

To this end, we have 4 groups of participants who are in this protocol: 1) children, 2) parents of these children, 3) Community Advisory Board (CAB) members, and 4) Parent Advisory Team (PAT) members. Some members of the CAB and PAT, are both involved in the conducting the research and are research subjects who will be completing the mixed-methods evaluation as indicated in the CAB and PAT consent forms [NOTE: PAT members may NOT be simultaneously enrolled at participants in the childhood obesity treatment program].

Background

1. Provide the scientific background, rationale and relevance of this project.

A. Background

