Community Advisory Board members were identified and named when the PCORI application was submitted:

- Representatives from organizations in the Dan River Region who have a child-focused organizational mission, invited as a stakeholder
- ≥18 years of age
- Willing and able to provide informed consent

Parent Advisory Team members:

- Parent who previously participated in a childhood obesity program and/or are the parent of a child ages 5-12 years of age
- ≥18 years of age
- live in the Dan River Region

2. List the criteria for exclusion

Parent/child dyads:

- children with a major cognitive impairment based on medical record review or contraindications for physical activity
- families that are already participating in a childhood obesity treatment program

Community Advisory Board: none

Parent Advisory Team:

- Cannot simultaneously be enrolled in the comparative effectiveness trial and serve on the Parent Advisory Team

3. List any restrictions on use of other drugs or treatments.

Parent/child dyads

- families that are already participating in a childhood obesity treatment program will be excluded

Community Advisory Board and Parent Advisory Team: NA

Statistical Considerations

1. Is stratification/randomization involved?

Yes

► IF YES, describe the stratification/ randomization scheme.

We will use simple randomization, at the parent-child dyad level. Randomization is not blinded. The researchers will have access to the randomization scheme.

► IF YES, who will generate the randomization scheme?

Sponsor
 UVa Statistician. Answer/Response:

UVa Investigational Drug Service (IDS)
 X Other: [name], statistician from Virginia Tech

2. What are the statistical considerations for the protocol?

- The primary end-point is 6-month reduction in BMI z-score.
- We calculated a standardized effect size relative to the differences in BMI z-scores and standard deviations *related to 6-month BMI z-score reduction* for *Family Connections* (0.07) and *Bright Bodies* as a target for the *iChoose+* condition (BMI z-score reduction = 0.16).

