- Follow-up assessments (3, 6, 12 months) will be scheduled by trained research staff. All assessments will be completed by a trained research staff member, following an established protocol from our manual of procedures (developed for our planning grant). All data will be collected and included in a single de-identified study data set and will not require linking of the electronic health record with study data (**IR-1; IR-2**). Questionnaires will be either orally administered by a trained researcher or completed via a computer-audio assisted assessment. Data completion checks will be completed for each participant at each assessment point and information that was missed inadvertently will be completed with the participant unless the participant explicitly decided to not complete a measure (**MD-1**). The 3-month assessment will only include height and weight (to calculate BMI percentile rankings for children) for children. Adult participants will be assessed for weight/height and complete a brief interview to provide feedback on the program. Demographics will only be assessed at baseline. Descriptive, parametric, and non-parametric statistical methods will be used to compare continuous and categorical variables among the intervention groups at baseline. Data will be examined for the presence of outliers, violations of normality (for those continuous variables) and missing data. Major violations of normality will be corrected with an appropriate transformation procedure. Missing data will be handled multiple ways through not only last-observation-carried-forward simple imputation but also Bayesian multiple imputations, Heckman sample selection models and a newly validated multiple imputation approach that incorporates Heckman selection as an imputation model (**MD-2; MD-3**). The maximum likelihood selection methods such as Heckman sample selection model are expected to be more efficient than multiple imputation methods while providing direct ways to test the underlying behavioral factors that drive missingness in the data. However, it is limited to missing outcomes relative to covariates are common in intervention trials. Therefore we will also do Bayesian multiple imputation and the multiple imputation combined with Heckman model as proposed by Galimard and colleagues.⁹⁸ In addition, based on the CONSORT guidelines for non-pharmacological trials, we will track participant dropout across each aspect of the trial and report on the number, proportion, and demographic characteristics

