ALL of the following procedures are being done for research purpose.

SEE ATTACHMENTS:

1. Parent Survey
2. Child Survey
3. Summative evaluation_iChoose parents
4. Summative evaluation_iChoose child
5. Summative evaluation_Family Connection parents
6. Summative evaluation_Family Connections child
7. CAB_PCORI_Capacity Eval QUANT survey
8. CAB_PCORI_Capacity Eval Qualitative survey
9. PAT_PCORI_Capacity Eval QUANT survey
10. PAT_PCORI_Capacity Eval Qualitative survey

Parent/Child Dyads.

The following health assessment will occur at baseline, 6-month and 12-month assessments among both the children ages 8-12 and parents.

- Height
- Weight
- Blood pressure
- Waist circumference
- Self-reported questionnaires (Parent Survey and Child Survey), pertaining to
 - Eating habits
 - Physical activity habits (via computer)
 - Quality of life/Health status (via computer)
 - Health literacy (via pencil/paper)
 - Home environment (parents only)(via computer)

At the 3-moth assessment: only height and weight are collected for parent and children. Parents will also complete a brief interview (PCORI 3 month assessment) examining program satisfaction, adherence, and retention.

At 6- and 12-month assessments: Post-program evaluation, quantitative ratings and qualitative interview.

For children ages 5-7, the Child Survey will be abbreviated to those measures validated for this age range. As such, only anthropometric data (height, weight, blood pressure, and waist circumference) and the Quality of Life questionnaire (as described on the 'Child Survey') will be collected. Assistance with computer administered surveys will be

IRB-HSR # 19748: A randomized-controlled trial to compare the reach, effectiveness and maintenance of two family-based childhood obesity treatment programs in a medically underserved region

provided for this age range by the research staff. Children 5-7 will also receive the same qualitative interviews at 6 and 12 months as the 8-12 year olds.

NOTE: Due to COVID-19 social distancing regulations an amendment to this protocol expands questionnaire data collection for parents and children (8 years-12 years) to mailed paper and pencil modality. This modality will only apply to Cohort 3 12 month follow-up data. Assistance with reading the survey over the phone will be offered to those who request this service. Researchers will explore the data for response differences at this time point to help determine any undue impacts from this change.

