- For those CAB members who are also part of the childhood obesity treatment program recruitment and implementation team, there will be regular monthly meetings, which include training aspects. Intervention will be delivered by program coordinators at Danville Parks & Recreation with an undergraduate degree in wellness, physical education, nutrition, or a related degree. Training for intervention delivery will be completed using a consultation approach that achieved fidelity to intervention activities at a rate exceeding 90%. ⁶⁶⁻⁶⁸ Lesson plans, scripted PowerPoint assisted session materials, and fidelity checklists will be used to increase the likelihood of consistent delivery of each intervention as intended. In addition, intervention components facilitated by interactive voice response technology will be monitored by the program coordinator.
- The academic team will also meet monthly with the Parent Health Advisors to provide oversight for the parent members who are playing a supportive role to assist families to overcome barriers to attendance, call completion, and maintenance of changes). Prior to the interventions starting, the training program will consist of a ~36 hours program that will incorporate didactic education, experiential and role playing instruction, peer-mentoring, and observation. A UVA research member residing in the region ([name]), is assigned to monitor the day-to-day activities of this group.

IRB-HSR # 19748: A randomized-controlled trial to compare the reach, effectiveness and maintenance of two family-based childhood obesity treatment programs in a medically underserved region

- Both groups will meet using a mix of in-person and conference call meetings and use a shared-decision making and participatory agenda meeting structure to guide all aspects of the study. As required by our PCORI funding agency, our intent is to engage these influential partners in all aspects of planning the research, conducting the research, and disseminating findings.

3. How do you plan to access any study records the non-UVA personnel might maintain?

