All outcome data will be maintained by UVA personnel. The screening data that is primarily maintained by SOVAH Pediatrics and PATHS personnel will be retrieved in-person on a monthly basis, or earlier if needed, based on the status of recruiting process. If needed more frequently than monthly, screening data may also be faxed directly to the UVA researchers or mailed. The process, field notes maintained by the Parent Advisory Team, will also be retrieved on a monthly basis during regular team meetings.

4. Will the non- UVA personnel be exposed to any additional risk while working on this protocol?

No.

5. List name of any other institution with which they have an affiliation.

Non-UVA study team members have affiliations listed above.

6. Will the non- UVa personnel have access to UVa patients or their health information along with any HIPAA identifiers prior to consent?

These are not UVA patients. However, the only non-UVA personnel that will have access to HIPAA identifiers prior to consent are the nurses who are helping with screening at SOVAH Pediatrics and PATHS and the Parks & Rec program leader staff (all who have passed CITI certification) who may assist in telephone screenings after the initial contact by SOVAH Pediatrics or PATHS.

YES	NO	
X		1. Name
X		2. All geographic subdivisions smaller than a state, including street address, city, county, precinct, zip code, and their equivalent geocodes, except for the initial three digits of the zip code if, according to the current publicly available data from the Bureau of the Census: (1) The geographic unit formed by combining all zip codes with the same 3 initial digits contains more than 20,000 people and (2) The initial 3 digits of a zip code for all such geographic units containing 20,000 is changed to 000.
X		3. All elements of dates (except year) for dates directly related to an individual, including birth date, admission date, discharge date, date of

		death; and all ages over 89 and all elements of dates (including year) indicative of such age, except that such ages and elements may be aggregated into a single category of age 90 or older. [This means you may record the year but not record the month or day of any date related to the subject if the subject is under the age of 89. In addition if the subject is over the age of 89 you may not record their age and you may not record the month, day or year of any date related to the subject]
X		4. Telephone numbers
	X	5. Fax numbers

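### The plan does not mask the staff who measure height and weight for the primary outcome, and the same assessments include interviews and arm-specific forms about the programme

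*Combined protocol and SAP*

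**What the plan says.** - **Allocation.** Statistical Considerations, item 1: "Randomization is not blinded. The researchers will have access to the randomization scheme". No exception is made for those who take outcome measurements.
- **Measurement.** Statistical Considerations, item 2: "All assessments will be completed by a trained research staff member, following an established protocol from our manual of procedures". This covers the child's height and weight, from which the primary endpoint is derived.
- **Content of the assessments.** Biomedical Research, item 2, on 3 months: "Parents will also complete a brief interview (PCORI 3 month assessment) examining program satisfaction, adherence, and retention". At 6 and 12 months there is a post-programme evaluation with ratings and an interview. The attachment list in the same item has separate summative evaluation forms for iChoose and for Family Connections. Neither the order of procedures within an assessment nor who conducts each one is given.
- **Delivery.** The training text for non-UVA personnel: "Intervention will be delivered by program coordinators at Danville Parks & Recreation". Item 3 of that section adds: "All outcome data will be maintained by UVA personnel".
- **Overlap.** Brief Summary/Abstract: "Some members of the CAB will be responsible for screening, recruit, enrollment/data collection, and program implementation and are included as study investigators".

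Nothing in the documents masks the measurers or keeps the scheme from them.

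**The concern.** Both programmes are open to families, so masking of participants is not at issue. Masking of the person at the stadiometer and scale is a separate matter, and the plan is silent on it. Height and weight still leave some judgement to the measurer: posture, clothing, rounding, and whether to repeat a reading. If those choices lean differently by arm after allocation, the lean enters the primary contrast. The expectation also has a direction, because the stated hypothesis is a larger reduction with iChoose+.

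Two features add to this. An interview or evaluation form about the programme would reveal the arm if it came before the measurement, and nothing prevents that order. The Abstract also allows one person to have a part in both implementation and data collection.

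**Working it through.** **1. Is access established?** Item 1 gives access to the researchers, and item 2 has research staff measure. The documents do not say outright that the measurers hold or consult the list. Since no exception is made, it is a fair inference that they could.

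**2. Are measurers and deliverers separate?** Three statements have to be read together:

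| Place | Role described | Who |
|---|---|---|
| Statistical Considerations, item 2 | all assessments | trained research staff |
| Training text, non-UVA personnel | delivery | Parks & Recreation coordinators |
| Brief Summary/Abstract | data collection and programme implementation | some advisory board members |

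The first two suggest largely separate groups. The third does not fit with full separation. That outcome data are held by UVA personnel concerns custody, not who measures.

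**3. Could the planned model remove the error?** In the primary model (Statistical Considerations, item 4) the treatment effect is θ, the coefficient of treatment group by time. A measurement error common to both arms cancels. An error that differs by arm at follow-up has the same form as θ. Neither the random effects nor the sensitivity analyses on their distribution can tell the two apart.

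**4. How large might it be?** The plan gives no figure for assessor error, so there is nothing to reproduce, and what follows is illustration only.

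Inputs:
- Target difference, from item 2: 0.16 − 0.07 = 0.09 BMI z.
- Completers at 6 months, from item 3: 64 per arm.
- SD of change: not stated, so back-calculated in two ways. From the stated effect size, 0.09 / 0.73 = 0.123. From the stated group sizes, 58 per arm for 80% power and 64 for 85% correspond to effect sizes of about 0.52 and 0.53 (two-sided t-test), and 0.09 / 0.53 = 0.17. The mismatch between 0.73 and those group sizes is a separate question. Here it only sets a range.
- Differential error b: assumed at 0.01, 0.02 or 0.03 BMI z.

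Share of the target: 0.01 / 0.09 = 11%; 0.02 / 0.09 = 22%; 0.03 / 0.09 = 33%.

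Standard error = SD × √(2/64), which is 0.0218 for SD 0.123 and 0.0300 for SD 0.17. With no true difference, the two-sided 5% two-sample t-test rejects with the power that belongs to a shift of b / SE (126 degrees of freedom):

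| b | share of 0.09 | b / SE, SD 0.123 | false positives | b / SE, SD 0.17 | false positives |
|---|---|---|---|---|---|
| 0 | 0% | 0 | 5% | 0 | 5% |
| 0.01 | 11% | 0.46 | 7.4% | 0.33 | 6.3% |
| 0.02 | 22% | 0.92 | 14.9% | 0.67 | 10.1% |
| 0.03 | 33% | 1.38 | 27.7% | 1.00 | 16.8% |

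Check of one cell by the normal approximation (b = 0.02, SD 0.123): Φ(−1.96 + 0.918) + Φ(−1.96 − 0.918) = 0.149 + 0.002 = 0.151, against 0.149 by the t-test.

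The planned analysis is a mixed model, not this test, so the table shows the order of size only.

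**The case against.** The case against has real weight.

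- Height and weight are objective, and staff follow a manual of procedures. That manual is not among the documents, and it may well govern clothing, posture, rounding and repeats. This stands, and it is why the low end of the table is the more plausible.
- The documents do not show that measurers see the list, that any interview comes before measurement, or that one person does both. The 3-month interview is not described as arm-specific, and 3 months is not the primary time point. This also stands. The point is that the plan leaves all of it open, including at 6 months, where the listed evaluation forms do differ by arm.
- Families know their programme and may say so. Masking would be imperfect, but incomplete masking is still better than none.
- Both arms are active programmes and the team has worked with both, so a motive to favour one should not be overstated. The stated hypothesis nevertheless favours iChoose+.

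A reader might infer from the training text that delivery staff are a wholly separate group, so that full masking would need nobody extra. The documents do not support that. The Abstract assigns some advisory board members to both kinds of work. The academic team meets monthly with the parent advisors who support families, and a UVA research member monitors those advisors' daily activity. No headcount or visit rota is given, and cohort 3 adds a second site.

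**Conclusion.** The point holds as a gap in the plan that is cheap to close. Measurers of the primary outcome are not masked by any provision, allocation is open to the researchers, and programme interviews and arm-specific forms belong to the same assessments with no set order. The planned model cannot correct an error that differs by arm.

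Its size is unknown. On the assumed errors of 0.01 to 0.03 BMI z, the false-positive rate would move from 5% to between about 6% and 28%, depending on the error and on a back-calculated SD of 0.17 to 0.123. A reader might take the upper figures as an estimate of bias in this trial. They are not: the error sizes are assumptions, and with an objective measure under a manual the true error may be near the low end or absent. The conclusion also rests on the inference that measurers are among the researchers with access.

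**What to change.** - At 3, 6 and 12 months, measure and lock height and weight before any programme interview or evaluation form.
- Do not give the measurers the allocation list, and say so in Statistical Considerations, items 1 and 2.
- Where existing staffing allows, roster as measurers only staff with no delivery or family-support role. Where it does not, say why.
- Ask families beforehand not to mention their programme, and log each unmasking.
- Reconcile the Abstract, Statistical Considerations item 2 and the training text on who collects outcome data and who implements the programmes.

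The document carries a version date of 04/22/2020, and cohort 3 was planned to start in 2/2019, so on the stated timeline the 6-month assessments had already fallen due. For measurements already taken, the remedy is to report whether measurers knew the allocation and whether any of them also delivered a programme.

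**Cost.** Visit order and list access are procedural changes that need no added staff. Rostering may be constrained with two sites, and masking will stay imperfect because families know their programme.

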Family Connections. This intervention condition was developed using an integrated research-practice partnership with a goal to develop an evidence-based program that would be practical and attractive to families, and would match the resource availability for sustained delivery.⁴² The intervention was based on the work of Golan and associates because the model:²⁵ (1) stressed a health-centered, rather than weight centric, approach; (2) demonstrated short and long-term effectiveness in reducing child BMI z-scores; (3) demonstrated effectiveness in improving parental health, and; (4) demonstrated that effectiveness in reducing child eating disorder symptoms.

Family Connections (the resultant program) highlights the need to address parental cognitive and behavior change, home environment change, and parental modeling of healthy behavior.⁴² Strategies included 2, 2-hour sessions and targeted about 10-25 parents representing distinct children. As in our previous trial both parents of a given child will be welcome to attend, but only one parent will be identified as the point of intervention and parental data collection. Parents will also receive 10 follow-up sessions delivered via IVR. The calls will be completed with high frequency initially and then scaled back over time (i.e., 2-3 calls per month during months 1-3 and then 1 call per month during months 4-6).

For cohorts 1-2 these programs will be implemented at one Danville, Virginia site via space provided by Danville Parks and Recreation subcontracted partner. For cohort 3 the study will expand to include both this Danville site and a Chatham, Virginia site with space rented through the Pittsylvania County Parks and Recreation.

Community Advisory Board and Parent Advisory Team. Both groups will meet monthly (e.g. using a mix of in-person and conference call meetings) and use a shared-decision making and participatory agenda meeting structure to guide all aspects of the study. The POPS and POPS-PAT groups will also meet together, as necessary, likely on a quarterly or bi-annual basis, to share ideas and report progress. As required by our PCORI funding

IRB-HSR # 19748: A randomized-controlled trial to compare the reach, effectiveness and maintenance of two family-based childhood obesity treatment programs in a medically underserved region

agency, our intent is to engage these influential partners in all aspects of planning the research, conducting the research, and disseminating findings.

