
of those lost to attrition and the reasons for attrition, when at all possible (**MD-4**).

NOTE: Due to COVID-19 social distancing regulations an amendment to this protocol expands questionnaire data collection for parents and children (8 years-12 years) to mailed paper and pencil modality. This modality will only apply to Cohort 3 12 month follow-up data. Assistance with reading the survey over the phone will be offered to those who request this service. Researchers will explore the data for response differences at this time point to help determine any undue impacts from this change.

- Interim analysis will occur after each of the three cohorts complete the 6-month assessment. Early stopping does not clearly apply to this trial, as there are no clear negative consequences. The extensive bibliography provided indicates the value of childhood obesity treatment programs and the minimal risk involved in such programs. Even if the primary outcome (child BMI z-score) does not show statistical improvements, other secondary end points may improve.

3. Provide a justification for the sample size used in this protocol.

Based on the relative BMI z-score differences and standard deviations related to 6-month BMI z-score reduction for *Family Connections* (0.07) and *Bright Bodies* we hypothesize an effect size of 0.73 (moderate to large effect) favoring *iChoose+*. To detect a significant difference between conditions, 58 or 64 children per group are needed to achieve 80% or 85% power with alpha of 0.05, respectively. When considering a typical attrition of 25% in this population, we project a sample size of ~87 participants is needed per condition (n=174 total) to achieve 85% power with approximately 64 dyads/condition completing 6-month assessment. Retention of families in our planning grant is currently 70% at 6-month follow-up.

4. What is your plan for primary variable analysis?

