Primary Aim: Multi-level mixed effect models will be employed to control errors of non-independence, heteroskedasticity caused by individual and family heterogeneity, and potential covariates needed to be controlled for in order to detect the pure BMI z-score reduction differences between the two conditions. In its simplest form, the model generally can be shown as: $BMIzscore_{ijt} = a_j + X'_{ijt}\beta + \gamma d_j + W'_j\delta_j + \tau T_t + \theta d_j \cdot T_t + \mu_i + \nu_{it}$. All measures are obtained for 4 time periods: baseline, 3-, 6-, and 12-months. The family-level intercept, a_j , is allowed to vary by parent-child-dyads and to be a random variable. The X s are the individual child-level covariates and the W s are family-level covariates. The model also contains treatment group indicators, d_j , and time period indicators, T_t . Relative treatment effect between conditions will be captured by coefficient θ . Individual child-level unobserved heterogeneity that is time invariant is represented by μ_i (**IR-5**). Sensitivity analysis will be conducted to examine the robustness of the mixed effect model across different random-effect distribution specifications (e.g., normal, finite mixture of normal etc.). Our study is powered to detect the average treatment effect at 6 months since the main interest of the POPS-

IRB-HSR # 19748: A randomized-controlled trial to compare the reach, effectiveness and maintenance of two family-based childhood obesity treatment programs in a medically underserved region

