A letter of support is provided from SOVAH Pediatrics and PATHS.

Biomedical Research

1. What will be done in this protocol?

Parent/Child Dyads.

Families have an equal chance of being randomly assigned to any one of the two programs. They cannot choose to which program they are assigned.

GROUP 1: iChoose

The iChoose program will last for 12 months. During the first six months families will be asked to:

- Attend 12 small group education sessions every other week. The health classes are for both the parent and child and will include information on nutrition and exercise.
- Attend one hour family exercise sessions two times a week (total of 48 sessions, 12 of which are part of the small group education sessions)
- Complete 12 automated telephone calls to provide support to help families reach your eating and physical activity goals.
- The child will also get 12 mailed newsletters to help them meet their program goals.

During the last six months of the program parents will continue to get support calls every other week (a total of 12 more calls) and your child will get 12 more newsletters.

See additional study procedures listed in #2 below.

GROUP 2: Family Connections

The Family Connections program will last for 6 months. During this time parents will be asked to:

- Attend 2 education sessions that are one week apart. The health classes are for parents/guardians only and will include information on parental role modeling regarding healthy nutrition and exercise behaviors.
- Complete 10 automated telephone calls to provide support families reach your eating and physical activity goals. There will be 2-3 calls per month during months 1-3 and then 1 call per month during months 4-6.

Community Advisory Board and Parent Advisory Team. Meeting procedures provided above in the study design section. (NOTE: the meetings are not part of the research procedures, only the mixed-methods evaluation, as described below. The participation in meetings is a contractual arrangement for advisory board members).

2. List the procedures, in bullet form, that will be done for RESEARCH PURPOSES as stipulated in this protocol.

IRB-HSR # 19748: A randomized-controlled trial to compare the reach, effectiveness and maintenance of two family-based childhood obesity treatment programs in a medically underserved region

Interventions: The iChoose and Family Connections interventions are described above and in the study design section.

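### The sample-size paragraph does not reconcile: an effect size of 0.73 at alpha 0.05 needs 31 or 35 children per group for 80% or 85% power, not 58 or 64

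*Combined protocol and SAP*

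**What the plan says.** Under Statistical Considerations, item 2, the plan states: "The primary end-point is 6-month reduction in BMI z-score". It describes the basis for planning as follows: "We calculated a standardized effect size relative to the differences in BMI z-scores and standard deviations". The reductions named there are 0.07 for Family Connections and 0.16 for iChoose+, the latter borrowed from Bright Bodies. Standard deviations are mentioned but no value is printed.

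Item 3 gives a standardized effect of 0.73 in favour of iChoose+ and then the requirement: "58 or 64 children per group are needed to achieve 80% or 85% power with alpha of 0.05, respectively". It applies 25% attrition to reach about 87 per condition (174 in total), with about 64 per condition expected to complete the 6-month assessment. It adds that 6-month retention in the planning grant was 70%.

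Item 4, the primary analysis, relies on this calculation: "Our study is powered to detect the average treatment effect at 6 months". It names non-independence as a reason for using mixed models, but gives no intraclass correlation or design effect.

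**The concern.** Effect size, alpha, power and group size are tied together by one formula, so any three fix the fourth. Here all four are printed and they disagree by nearly a factor of two, too much for rounding or choice of software to explain.

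This paragraph is the only justification for 174 dyads. As written, a reader cannot tell what difference 64 completers per group were meant to detect. That matters most if the result is null, because the reader then needs to know whether the trial could have seen a difference of about 0.066 BMI z or only one of about 0.09.

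**Working it through.** **Inputs.** From item 3: effect size d = 0.73, alpha 0.05, power 80% and 85%, attrition 25%, planning-grant retention 70%. From item 2: reductions of 0.07 and 0.16, a difference of 0.09. Allocation is 1:1 (Biomedical Research, item 1). A two-sided test is my assumption.

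**1. Trying to reproduce 58 and 64.** The normal approximation is n per group = 2(z₁₋α/₂ + z₁₋β)² / d².

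- 80%: 2 × (1.960 + 0.842)² / 0.73² = 29.5, so 30.
- 85%: 2 × (1.960 + 1.036)² / 0.73² = 33.7, so 34.

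The exact two-sample t-test gives 30.45 and 34.68, so 31 and 35. One-sided it gives 23.9 and 27.7, so 24 and 28, which widens the gap. Reading 58 and 64 as totals does not work either: the totals would be 62 and 70.

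**2. Power that the printed counts would give at d = 0.73** (two-sided t-test).

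| n per group | Stated power | Computed power |
|---|---|---|
| 58 | 80% | 97.4% |
| 64 | 85% | 98.4% |

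**3. What could lie behind 58 and 64.** The ratio 64/58 is 1.10, while the t-test requirement at 85% over that at 80% is 34.68/30.45 = 1.14. At alpha 0.05, therefore, one smaller effect size or one constant inflation can only come close.

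- *A smaller effect.* d = 0.53 needs 56.9 and 64.9, so 57 and 65. At d = 0.53, 58 per group gives 80.8% power and 64 gives 84.5%.
- *An inflation factor.* 58/30.45 = 1.90 and 64/34.68 = 1.85. Sessions are delivered in groups: the Family Connections sessions "targeted about 10-25 parents representing distinct children", and iChoose families are to "Attend 12 small group education sessions every other week". With design effect = 1 + (m − 1) × ICC, and assuming the same group size m in both arms, m = 10 needs an ICC of 0.85/9 to 0.90/9, about 0.094 to 0.10. For m = 25 it is 0.85/24 to 0.90/24, about 0.035 to 0.038. No ICC is given, and no size is given for the iChoose groups.
- *A smaller alpha.* d = 0.73 at two-sided alpha 0.05/19 ≈ 0.0026 needs 57.9 and 63.7, so 58 and 64. This fits exactly but contradicts the printed alpha of 0.05.

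**4. Implied SD and detectable difference.** SD = 0.09/d, so 0.09/0.73 = 0.123 and 0.09/0.53 = 0.170. With 64 per group, 85% power and two-sided alpha 0.05, the detectable standardized effect is 0.534.

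- SD 0.123, no inflation: 0.534 × 0.123 = 0.066 BMI z.
- SD 0.170: 0.534 × 0.170 = 0.091 BMI z. If 0.73 was used with an inflation of about 1.85, the detectable difference is also about 0.09.

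**5. The attrition step.** 64/0.75 = 85.3, and 87 × 0.75 = 65.25, so about 87 is consistent with the stated 25%. At the 70% retention seen in the planning grant, 87 × 0.70 = 60.9 completers per group. Power is then about 98% at d = 0.73 with no inflation, but about 83% at d = 0.53.

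**The case against.** The strongest reply is that no printed number need be wrong. The programmes are delivered in groups and three interim analyses are planned, so a careful statistician might have inflated the sample for clustering or used a stricter alpha and simply not recorded it. The smaller-alpha route reproduces 58 and 64 exactly, while d = 0.53 is one child out on each count, so the printed 0.73 may well be correct.

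That stands as a caution. The fault may be a missing input rather than a wrong figure, and 0.53 should not be substituted without evidence. It does not rescue the paragraph. It prints alpha 0.05 with no adjustment, and no ICC or design effect appears anywhere in the plan. The primary model has random terms for the dyad and child but none for the session group, so nothing there signals that clustering entered the planning.

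A second reply is that the discrepancy is conservative and comes too late to change the sample: this version is dated April 2020, after the last cohort's intervention was due to end. Both points are fair and bear on urgency. But the discrepancy is conservative only if 0.73 is right with no inflation, and the power statement will still be used to interpret the result.

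**Conclusion.** The concern holds. On the stated inputs the requirement is 31 or 35 children per group (two-sided t-test assumed, 1:1 allocation), and the printed 58 or 64 are 1.85 to 1.90 times that. Either a printed figure is wrong or an input has been left out, and the documents do not show which.

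The consequence is an uncertain design target: 64 completers per group give 85% power for about 0.066 BMI z on one reading and about 0.09 on the others. The trial is not shown to be underpowered. The attrition step agrees with the stated 25%, although the 70% retention quoted beside it would leave about 61 completers per group, fewer than the 64 the plan counts on.

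**What to change.** Go back to the original power calculation and rewrite the paragraph so that effect size, group size and power agree. State the SD of 6-month BMI z-score change, the test, its sidedness, the alpha actually used and any inflation factor. Then:

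- if 0.73 is right and neither an inflation nor a smaller alpha was used, restate power as about 98% with 64 completers per group;
- if the counts came from a smaller effect, replace 0.73 with the value used (about 0.53 on the arithmetic above);
- if an inflation was used, state it with the ICC and group size behind it;
- if a smaller alpha was used, state it and the reason.

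The cost is one corrected paragraph. Enrolment, data collection and analysis do not change.
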